**Safety Data** 

AE and AE mitigation data will be summarized with descriptive statistics, by type of SMF reduction treatment, system organ class (SOC), and preferred term (PT), and presented in listings. The duration (days) and severity of pain, swelling, and bruising will be summarized by type of SMF reduction treatment, by treatment session, and overall. When a patient has an occurrence of a PT more than once, the patient's average duration for the PT will be computed for the overall summary. Pain scores from the Pain Numeric Rating Scale will be summarized with descriptive statistics by type of SMF reduction treatment and time point.

#### **DATA FOR COLLECTION**

	Site Screening	Enrollment (all patients)	Baseline (treated patients)	Follow-up (treated patients)	End-of-Study (untreated patients)	End-of- Treatment (treated patients)
Physician Practice Setting Questionnaire a	X					
Patient Population Informed consent / medical records release /brief medical history Demography & Clinical Information Patient Treatment History Patient Treatment Goals Questionnaire Physician Treatment Goals Questionnaire		X X f X X			X f	X f
Treatment Logistics: Treatment Logistics Questionnaire Pain Numeric Rating Scale Treatment Procedures Questionnaire			X b X e X c	Xe		X e
Adverse Events: Adverse Event Log			$X^{b}$	$X^{b}$		X b
Treatment Outcomes & Follow-up:  SMF assessments:  Clinician-Reported Submental Fat Rating Scale (CR-SMFRS) score Patient-Reported Submental Fat Rating Scale (PR-SMFRS) score Patient-Reported Submental Fat Impact Scale (PR-SMFIS) score Submental Skin Laxity Grade (SMSLG) Subject Self Rating Scale (SSRS) Patient Self-Perception of Age (SPA) scale Patient Global Questions (PGQ) Patient End-of-Treatment Questionnaire Physician End-of-Study Questionnaire Patient End-of-Study Questionnaire		X X X X X		$egin{array}{c} X^b \ X^b \ X^b \ X^b \ X^b \ \end{array}$	X d	X b

- a: Physician Practice Setting Questionnaire is to be completed once for each site at the start of the study (following site initiation).
- b: To be completed only for patients who elect a SMF reduction treatment (treated patients). (Applicable time points: Baseline, Follow-up, End-of-Treatment).
- c: To be completed only for patients treated with ATX-101. (Applicable data point(s): Treatment Procedures Questionnaire).
- d: To be completed only for untreated patients. (Applicable data point: Patient End-of-Study Questionnaire)
- e: To be completed only for patients who elect a SMF reduction treatment (treated patients) at the following applicable time points: Baseline, Follow-up, and End-of-Treatment. Patients treated with ATX-101 will be asked to provide pain scores at each ATX-101 treatment visit.
- f: Demography (birth date, sex, race, ethnic origin) & Clinical Information (height, weight, lifestyle habits) to be collected at Enrollment; Clinical Information (height, weight) to be collected at End-of-Treatment / End-of-Study for all patients.

### ABBREVIATIONS AND ACRONYMS

AE adverse event

ANCOVA analysis of covariance

BMI body mass index
CI confidence interval

CMH Cochran-Mantel-Haenszel

CR-SMFRS Clinician-Reported Submental Fat Rating Scale

eCRF electronic case report form

EDC electronic data capture

GPP Good Pharmacoepidemiology Practices

HCP healthcare provider

ICF Informed Consent Form

IEC Independent Ethics Committee
IRB Institutional Review Board

ISPE International Society for Pharmacoepidemiology
MedDRA Medical Dictionary for Regulatory Activities
PR-SMFIS Patient-Reported Submental Fat Impact Scale
PR-SMFRS Patient-Reported Submental Fat Rating Scale

PT preferred term

SAE serious adverse event SAP Statistical Analysis Plan

SD standard deviation

SM Submental SMF submental fat

SMSLG Submental Skin Laxity Grade

SOC system organ class

SPA Self-perception of Age SSRS Subject Self Rating Scale

SUSAR suspected unexpected serious adverse reaction

#### 1 INTRODUCTION

# 1.1 Background

Submental (SM) fullness associated with the accumulation of submental fat (SMF) can influence negative self-perception. While the SM region is visually important, at present, only surgical options (cosmetic surgery, liposuction) are available for addressing SM fullness through SMF reduction, and not all patients are suitable candidates for, or willing to undergo, these invasive procedures and the potential complications. Currently available injectable products, ie, botulinum toxins and dermal fillers, are primarily employed in the aesthetic rejuvenation of the upper and mid-face and do not adequately address contouring the SM region. The use of energy based devices for lipolysis has been investigated as a less invasive approach, but may still require accompanying surgery in more severely affected cases, and safety concerns remain. Recently, a pharmacologic treatment, deoxycholic acid injection (ATX-101), was approved by the FDA for improvement in the appearance of moderate to severe convexity or fullness associated with submental fat in adults.

# 1.2 Study Rationale

This registry will gather information on use patterns and outcomes of treatments for addressing SM fullness through SMF reduction, beginning with currently used methods, and including newly approved products as they become adopted into the practice.

#### 2 OBJECTIVES

The primary objective of this registry is to develop a comprehensive understanding of the condition of SM fullness due to SMF, how it is treated in current clinical practice, and the risks and benefits associated with its treatment. This objective will be accomplished through the systematic collection of data on the following:

- Population of physicians with patients who have SMF concerns
- Population of patients who are eligible for SMF reduction treatment
- Eligible patients who elect SMF reduction treatment
- Treatment procedures
- Treatment outcomes
- Safety profile through adverse event reporting of the SMF reduction treatments administered

#### 3 STUDY CONDUCT

# 3.1 Design of the Study

This is a prospective, non-interventional, longitudinal, multi-center registry to be conducted in patients with SM fullness due to SMF. Each participating physician will prescribe treatments based on his or her usual clinical practice, and no restriction on the use of commercially available treatments will be imposed. As this is a non-interventional study, the patient-physician relationship will not be affected, nor will there be any influence on the therapeutic management of the patient.

Study visits, procedures, and evaluations are summarized in Data for Collection and described in detail in Sections 5 and 6.

Patients considering treatment to reduce SMF will be recruited. Eligible patients will be enrolled in the registry, and patients who elect treatment will be followed until their SMF reduction treatment is completed or discontinued. Patients who do not initially elect treatment will be followed to determine whether or not they subsequently undergo treatmentuntil up to one year has elapsed since enrollment and no treatment has been elected. Reasons for treatment discontinuation, or for the decision to not receive treatment, will be recorded. Enrolled patients will be assessed regularly by their treating physician according to usual clinical practice. Data collection is anticipated to continue for approximately 15 months. The duration of individual patient participation will vary depending on the chosen treatment method and individual requirements.

At Enrollment, relevant data on previous SMF and facial aesthetic treatments will be collected from the patients, and as necessary, from their medical records. Additionally, baseline assessments of SMF will be performed. Details of the investigator's practice setting will be recorded after site initiation, and details of treatment logistics will be recorded at the first treatment session(s) (for each treatment selected) for patients who elect treatment for SMF reduction . Information, including treatment received for SMF reduction, treatment procedures and outcomes, follow-up assessments of SMF, and adverse events (AEs) will be recorded at subsequent clinic visits or telephone contacts. Patient medical history data will be updated, as appropriate, at the first treatment session (Baseline Treatment Visit).

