Number of Patients	Approximately 1000 patients will be recruited from approximately 100 sites in the US and Canada.
Study Procedures	Details of the physician's practice setting will be recorded once for each site; treatment logistics will be recorded at the first treatment session for each patient.  Patients considering treatment for improvement of SM fullness due to SMF will be recruited. Eligible patients will be enrolled in the registry and data will be collected from patients who elect treatment until their SMF reduction treatment is completed or discontinued. Patients who do not initially elect treatment will be followed to determine whether or not they subsequently undergo treatment, and if not, until up to one year has elapsed since enrollment and no treatment has been elected. Physicians will treat and assess patients according to their discretion.  At enrollment, data on previous relevant SMF and facial aesthetic treatment(s) will be collected from the patients, and as necessary, their medical records, along with baseline SMF assessments and information on treatment goals. Demography (birth date, sex, race, ethnic origin), Clinical Information (height, weight, lifestyle habits), and a brief medical history (including diabetes, cardiovascular disease) will be collected, Information including treatment received for SMF reduction, treatment procedures and outcomes, follow-up assessments of SMF, and adverse events (AEs) will be recorded at subsequent clinic visits or telephone contacts (Data for Collection). Patient medical history data will be updated, as appropriate, at the first treatment visit.
Data Collection Procedures	Electronic data capture (EDC) will be used for participating sites to record clinical data, data questionnaires and assessment data via electronic case report forms (eCRFs) accessed through a secure internet portal. Data entry screens will be designed to efficiently capture the desired data elements from patient medical records (Data for Collection).
Data Elements	Physician Practice Profile At each site, the physician will complete the Physician Practice Setting Questionnaire, including the following information:  • Physician characteristics:  - Clinical history / specialty, including board certification  - Years of aesthetic practice  - Percent of practice focused on facial aesthetics  - Physician approach to discussing new treatment options  - Number and roles of physicians and other healthcare providers (HCPs) in the

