#### 5.1.4 Final Visit

The patient's Final Visit will take place either at the last scheduled follow-up visit after completion of all SMF reduction treatment(s), within 3 months of the last treatment session (for each treatment selected), when a patient elects to discontinue treatment, or prior to study closure (treated patients). Information on AE/SAEs, treatment outcomes, and End-of Study assessments will be recorded (section 5.3.4). For patients who do not elect treatment for SMF reduction (untreated patients), the reason for not selecting treatment will be captured at this time point.

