# **5.3.4** End-of-Study Assessments

The following information will be collected at the Final Visit(s), which should occur within 3 months after the last treatment session(s) for treated patients, at the discontinuation visit, or prior to study closure (for untreated patients) in order to capture patient and physician feedback regarding treatment decisions.

For patients who elect treatment for SMF reduction (treated patients), the following information will be captured at the Final Visit (End-of-Treatment):

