# 8 STATISTICAL METHODS

A formal statistical analysis plan (SAP) that will provide details of all analyses and presentation of registry data will be approved prior to database lock and data analysis.

Descriptive statistics will comprise the number of observations (n), mean, standard deviation (SD), median, minimum, and maximum for continuous variables; and n and percent for categorical variables, with the number of patients who do not have missing values as the denominator.

For this registry, no imputation for missing data will be performed. Analyses will be conducted using observed cases.

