# 9.8.4 Patients Lost to Follow-Up

Some proportion of patients may discontinue the study. Investigators will be encouraged to share the patient's data with him/her, in an effort to encourage the patient to remain involved in the study. Patients who do not choose a treatment for reduction of their SMF, or who withdraw treatment, will be asked to complete final visit assessments and record the reason in the Patient End-of-treatment Questionnaire. Steps may be taken to evaluate the presence of, and ameliorate, potential bias associated with differential attrition. Details will be provided in the Statistical Analysis Plan.

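### About 15 months of data collection gives the full one-year election window only to patients enrolled by about month 3, and the protocol contradicts itself on whether treated patients are cut off at study closure

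*Protocol*

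**What the plan says.** Section 3.1 makes three commitments about time. First, "Data collection is anticipated to continue for approximately 15 months". Second, patients who do not elect treatment at the start are followed until "up to one year has elapsed since enrollment and no treatment has been elected"; the Synopsis says the same. Third, "patients who elect treatment will be followed until their SMF reduction treatment is completed or discontinued".

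Two sections time the Final Visit, and they differ:

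- Section 5.1.4 lists, for treated patients, the last scheduled follow-up after all treatment is completed, a visit no more than 3 months after the last session, the point of discontinuing treatment, and a visit ahead of study closure.
- Section 5.3.4 describes the Final Visit as one "which should occur within 3 months after the last treatment session(s) for treated patients, at the discontinuation visit, or prior to study closure", and the parenthesis that follows these words limits the closure clause to untreated patients. For treated patients this section labels the Final Visit End-of-Treatment.

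On analysis, Section 8 says that "no imputation for missing data will be performed. Analyses will be conducted using observed cases", with percentages taken over patients whose values are not missing. Section 2 names eligible patients who elect treatment as part of the primary objective. Section 9.8.4 adds that "Steps may be taken to evaluate the presence of, and ameliorate, potential bias associated with differential attrition", and leaves the details to the SAP.

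**The concern.** The election window and the Final Visit lag, each at its maximum, already add up to the whole 15 months before any enrolment or treatment time is counted. Two results of the registry could be affected.

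The first is the share of patients who elect treatment. If enrolment runs past month 3, later patients are observed for less than a year. A plain count over enrolled patients then treats the end of observation as if it were a decision not to be treated.

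The second is response at End-of-Treatment. If treated patients can be closed out because the registry is ending, a patient part-way through a course of several sessions receives the same End-of-Treatment assessment as one who finished. Longer courses are the likelier ones to be cut, so a comparison by treatment type could partly reflect course length and enrolment date.

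**Working it through.** **Inputs.** From the protocol: T = 15 months of data collection (anticipated, approximate); election window up to 12 months; Final Visit up to 3 months after the last session; about 1000 patients at about 100 sites. Not in the protocol, so assumed: the enrolment period A, treatment duration t, and all election rates. The 15 months is not derived anywhere, so it can be compared with the other windows but not reproduced.

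**Calendar.** A full election window needs enrolment month + 12 ≤ 15, so enrolment by month 3. For everyone to have it, recruitment must run at 1000 / 100 / 3 = 3.3 patients per site per month from the first day.

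For a patient enrolled on day 0 who elects at month 12, with the maximum Final Visit lag, the time needed is 12 + t + 3. That is 15, 16, 19 and 21 months for t = 0, 1, 4 and 6. With the Final Visit at the last session it is 12 + t, which fits only if enrolment month + t ≤ 3.

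Patients treated at enrolment fare better. With t = 6 and a 3-month lag, the share that fits is (15 - 6 - 3) / A, capped at 100%: 100% for A = 6 and 50% for A = 12.

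**Election percentage.** Assume uniform enrolment over A months and a constant election hazard λ among initial non-electors, with λ = -ln(1 - 0.30) / 12 = 0.0297 per month for a true 12-month rate of 30%. The crude share is the mean of 1 - exp(-λ·min(12, 15 - e)) over e uniform on (0, A).

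For A = 12, one quarter of patients have the full window (30%). The rest have windows spread evenly from 12 down to 3 months. Their mean is 1 - (0.7^0.25 - 0.7) / (9λ) = 1 - 0.2147 / 0.2675 = 19.7%. The crude share is 0.25 × 30% + 0.75 × 19.7% = 22.3%. If half of all patients elect at once, the true overall rate is 0.5 + 0.5 × 0.30 = 65.0% and the crude one is 0.5 + 0.5 × 0.223 = 61.2%.

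| A (months) | Full 12 months | Initial non-electors, true 30% | All patients, 50% elect at once, true 65.0% | All patients, 80% elect at once, true 86.0% |
|---|---|---|---|---|
| 3 | 100% | 30.0% | 65.0% | 86.0% |
| 6 | 50% | 28.4% | 64.2% | 85.7% |
| 9 | 33% | 25.6% | 62.8% | 85.1% |
| 12 | 25% | 22.3% | 61.2% | 84.5% |
| 15 | 20% | 18.7% | 59.4% | 83.7% |

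**Who is cut off at closure.** Section 3.1 follows treated patients to completion or discontinuation and gives no closure exception. Section 5.1.4 includes closure among the occasions for a treated patient's Final Visit. Section 5.3.4 confines closure to untreated patients. These cannot all hold for a patient in mid-course when the registry ends.

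**End-of-Treatment response.** A simulation of 400,000 patients assumed that 60% elect at once and 30% of the rest elect within 12 months, with one to six monthly sessions, the Final Visit 3 months after the last session, and patients cut by closure counted as missing. The true rate was about 67.5%, the response rate Section 8.1 expects for the CR-SMFRS. For A = 12 the observed rate was 67.5% if response was unrelated to the number of sessions, 64.6% if it rose with sessions and 70.4% if it fell. For A = 6 the shift was about 0.4 points either way. If cut-off patients are instead assessed early, the error is of another kind, and the protocol gives nothing from which to size it.

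**The case against.** The strongest reply is that the windows are ceilings. The one year and the 3 months are both maxima, the 15 months is approximate and anticipated, and individual participation is expected to vary. Sites are chosen for high volume, the 1000 is an upper figure in Section 8.1, and the sponsor may stop enrolment at any time, so enrolment within 3 months is not shown to be infeasible. This stands. A reader might infer that the design cannot fit into 15 months at all, but the documents support that only for late electors at full windows and for non-electors enrolled after about month 3.

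A reader might also infer that the plan already counts a patient cut off early as a non-elector. It does not say so: no one-year election rate, denominator or estimator is defined, and a time-to-election analysis may be in the SAP, which is not shown. The downward bias follows only if the simple count-and-percent summary is used and read as a one-year rate.

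A third tempting reading is that leaving out patients without a score inflates response. The direction is not established, as the simulation shows. Counting missing scores as non-response would be no remedy, because it would build the closure cut-off into the rate.

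Finally, Section 9.8.4 does not conflict with the observed-case rule: attrition bias can be addressed without imputation, for example by weighting. That section concerns patients who discontinue, however, and does not settle the calendar or the closure rule.

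**Conclusion.** The point holds in limited form. Unless enrolment closes by about month 3, some non-electors cannot be observed for a year, and a crude election percentage read as a one-year rate is too low. Under uniform enrolment and a constant hazard, with a true 30% among initial non-electors, the shortfall in that group runs from 0 (enrolment over 3 months) to 7.7 points (over 12 months). Across all patients the 12-month figure shrinks to 3.8 points if half elect at once and 1.5 points if 80% do. The enrolment period and the election rates are assumptions; the protocol states none.

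The contradiction between Sections 3.1, 5.1.4 and 5.3.4 rests on no assumption. While it remains, End-of-Treatment response may combine completed and truncated courses, with a bias of unknown direction and size.

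**What to change.** 1. Reconcile Sections 3.1, 5.1.4 and 5.3.4 on who is cut off at study closure, and state when enrolment closes relative to the 15 months.
2. Report election as a 12-month Kaplan-Meier cumulative incidence, censoring at last contact or closure, with numbers at risk. The treatment decision dates listed in the Synopsis are enough for this.
3. Flag each End-of-Treatment record as completed, discontinued or closed mid-course, and tabulate End-of-Treatment response by that flag. Reasons for discontinuation are already recorded under Section 3.1, so the new information is mainly the closed mid-course category.

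The cost is protocol wording, one status field and slightly more analysis. The Kaplan-Meier estimate assumes that censoring is unrelated to the chance of electing. That is reasonable for closure if election does not drift over calendar time, and less certain for loss to follow-up, so the report should say so.

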# 3.2 Patient Discontinuation and Study Site or Study Termination

#### 3.2.1 Withdrawal of Individual Patients Prior to Study Completion

A patient may be withdrawn from the registry prior to completion, or the decision to not receive treatment, for any of the following reasons:

• Withdrawal of patient consent

• Any other reason, including lack of willingness to complete assessment questionnaires, the patient's best medical interest, or decisions made by the investigator or the sponsor

If a patient withdraws or is withdrawn, the reason should be documented in the electronic case report form (eCRF).

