#### 4 STUDY POPULATION

#### 4.1 Inclusion Criteria

A patient must meet all of the following criteria to be eligible for participation in the registry.

- 1. Adult male and female patients, aged 18 years and above, presenting with SM fullness due to the accumulation of unwanted SMF, and considered by their treating physician to be a candidate to receive treatment of SM fullness by reduction of SMF, if the patient decides
- 2. Signed informed consent by the patient, obtained before any study-related activities are undertaken
- 3. Willing to complete all patient assessment questionnaires
- 4. Signed release form by the patient, permitting abstraction of the patient's medical records at baseline and during participation in the registry

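### Section 3.2.1 lets a treated patient who still consents be withdrawn from the whole registry for declining questionnaires, which permits avoidable loss of later clinician ratings and non-serious AEs

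*Protocol*

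**What the plan says.** Section 3.2.1 opens with "A patient may be withdrawn from the registry prior to completion" and gives two grounds. The first is withdrawal of consent. The second is a catch-all: "Any other reason, including lack of willingness to complete assessment questionnaires, the patient's best medical interest, or decisions made by the investigator or the sponsor". The only action required on withdrawal is to record the reason in the eCRF.

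Section 4.1 makes willingness to complete the questionnaires an entry criterion: "Willing to complete all patient assessment questionnaires". It also requires a records release "permitting abstraction of the patient's medical records at baseline and during participation in the registry", so the release does not clearly extend past participation.

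Section 8 states that "no imputation for missing data will be performed. Analyses will be conducted using observed cases", and percentages use patients with non-missing values as the denominator. Section 8.2.1 takes as the analysis population all enrolled patients with at least one post-baseline visit.

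**The concern.** The rule ties the whole registry record to one part of it. CR-SMFRS is scored by the investigator after examination (Appendix 11.2), and SMSLG by an assessor (Appendix 11.1). The physician or designee completes the Physician End-of-Treatment Questionnaire (Section 5.3.4). AEs come from examination, open-ended interview and patient calls (Sections 5.3.2 to 5.3.4). A refused form makes none of these unobtainable.

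The registry is non-interventional (Section 3.1). A patient withdrawn over the forms may therefore carry on with treatment at the same practice while later sessions, ratings and events go unrecorded. The safety profile is part of the primary objective (Section 2). Section 8.2.2.3 plans summaries of the duration and severity of pain, swelling and bruising by session, and Section 8.2.2.1 uses SMSLG to look for an increase in skin laxity.

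Willingness to keep answering forms may depend on how treatment went. If it does, the observed cases are a selected group. An SAP can describe that selection, but it cannot recover ratings or events that sites were allowed to stop collecting.

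**Working it through.** **Step 1: the plan's own figure.** Table 1 (Section 8.1) takes an expected CR-SMFRS response of 67.5%. With half-width = 1.96 × √(p(1 − p)/N) and p = 0.675:

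- N = 250: 1.96 × √(0.219375/250) = 5.8 points, giving 61.7 to 73.3
- N = 500: 4.1 points, giving 63.4 to 71.6
- N = 750: 3.4 points (3.35 unrounded), giving 64.1 to 70.9

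All three intervals agree with Table 1. They express sampling error only.

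**Step 2: effect of selective loss.** Let w be the share of a treated cohort withdrawn on this ground before the End-of-Treatment rating, and d the amount by which their true response lies below 67.5%. The observed rate is (p − w(p − d))/(1 − w), so the shift is w·d/(1 − w). Neither w nor d is in the protocol; both are assumptions.

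| w | d = 0 | d = 20 points | d = 30 points |
|---|---|---|---|
| 2% | 0 | +0.4 | +0.6 |
| 5% | 0 | +1.1 | +1.6 |
| 10% | 0 | +2.2 | +3.3 |
| 20% | 0 | +5.0 | +7.5 |

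Example: w = 0.10 and d = 0.20 give (0.675 − 0.10 × 0.475)/0.90 = 69.7%, a shift of +2.2 points. If withdrawal is unrelated to response (d = 0), there is no shift at any w. If the withdrawn patients did better than the rest, the sign reverses.

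**Step 3: compared with the planned precision.** The shift equals the Table 1 half-width h when w = h/(d + h). With d = 20 points that is about 22% withdrawn at N = 250 (5.81/25.81), 17% at N = 500 and 14% at N = 750.

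**Step 4: limits without a direction.** If 67.5% is observed and a share w is missing, the full-cohort rate lies between 67.5(1 − w) and 67.5(1 − w) + 100w. That is 64.1 to 69.1 at 5%, 60.8 to 70.8 at 10%, and 54.0 to 74.0 at 20%.

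**Step 5: how much a fix can recover.** CR-SMFRS and SMSLG need the patient present. If half of a 10% withdrawn group would have stopped attending anyway, and had the same response gap, 5% remain missing after the fix. The residual shift is then the 5% row: +1.1 or +1.6 points. So the figures in Step 2 are upper limits on what the rule itself costs.

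**Step 6: do other sections close the gap?**

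- Section 9.8.4 asks for final assessments from patients who choose no treatment or withdraw from treatment. It does not name those withdrawn from the registry.
- Section 5.1.4 triggers the Final Visit when a patient elects to stop treatment. Section 5.3.4 mentions a discontinuation visit but does not say whether stopping treatment or leaving the registry is meant. At best it yields one last assessment.
- Section 6.3 requires reporting of AEs that lead to withdrawal, of deaths up to 30 days after the final visit, and follow-up of medically significant AEs. Section 6.4 covers SAEs, including follow-up queries after the study ends.
- No section provides for later clinician ratings, for new non-serious AEs, or for the duration of ordinary pain, swelling or bruising still present at withdrawal.

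**The case against.** The strongest reply is that the rule is permissive and compels no withdrawal. It also mirrors an entry criterion, so it is coherent rather than contradictory. That is right: this is a point about design, not an inconsistency.

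Three stronger readings are tempting, and the protocol does not support them.

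- **That safety follow-up ends or AE data are lost wholesale.** Nothing says recorded AEs are discarded, and Sections 6.3 and 6.4 keep the events listed in Step 6. A patient leaving because of a side effect is the case those provisions address most directly. What is exposed is non-serious AEs that start or continue after withdrawal.
- **That losses are selective and the rates are biased.** The protocol gives no withdrawal rate, no link with outcome and no direction. Only the possibility is established.
- **That attrition handling is missing.** Section 9.8.4 acknowledges differential attrition and leaves the details to the SAP, which is not at hand. The recorded withdrawal reason also lets these patients be identified.

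It is also fair that a patient who refuses forms may stop attending, in which case no rule recovers a rating, and that the study is descriptive with no pre-specified hypothesis. These points reduce the size of the problem. They do not answer the case of a patient who keeps attending and still consents.

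**Conclusion.** The point holds in limited form. Section 3.2.1 permits avoidable and possibly outcome-related loss of later CR-SMFRS and SMSLG ratings and of new or ongoing non-serious AEs, for a reason that is neither consent nor safety. With observed-case analysis this can bias the cohort rates.

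Size and direction are unknown. Taking 67.5% as the true rate, and assuming 10% withdrawn with response 20 to 30 points lower, the shift is about +2 to +3 points at most. That is smaller than the 5.8-point half-width at N = 250 and close to the 3.4-point half-width at N = 750 in the upper case. It is smaller with fewer withdrawals, larger with more, and zero if withdrawal is unrelated to response. This is an inexpensive improvement to a conduct rule, not a defect that undermines the registry.

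**What to change.** In Section 3.2.1:

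- Remove unwillingness to complete questionnaires from the withdrawal grounds. Deleting the phrase alone is not enough, because the catch-all and the investigator or sponsor decision clause would still allow the same withdrawal.
- Add that declining questionnaires is not by itself a reason for withdrawal, including under the catch-all.
- Add that, while consent stands, CR-SMFRS and SMSLG at visits that occur, AE/SAE collection and medical-record abstraction continue to the Final Visit, with patient forms marked 'declined'.

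In Section 5.3.4, state that the discontinuation visit also applies to patients withdrawn from the registry who agree to it. Inclusion criterion 3 stays as an entry condition only.

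The cost is a few protocol sentences and a 'declined' option on the patient-reported eCRFs. The downside is slightly more missing patient-reported data shown in the tables.
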